8.0. Biospecimen and Blood Pressure (BP) Substudy

To determine whether cocoa flavanols and/or a daily multivitamin use will significantly change levels of blood flavonoids, other pertinent nutritional biomarkers, vascular/metabolic biomarkers, and blood pressure from baseline, we will conduct a substudy in a sample of approximately 3,500 male and 3,500 female COSMOS participants who sign a separate consent for this additional procedure at baseline. COSMOS participants selected will either have baseline bloods and urine collected on their own through mailed blood kits that are returned by the participant, or have bloods, urine, BP, and brief anthropometric measurements collected and shipped through Examination Management Services, Inc (EMSI). As an alternative to EMSI, Quest diagnostic labs are available to assist with the specimen collections and shipments. A subgroup of these participants will also have follow-up samples and measurements collected again during follow-up using similar procedures. The total amount of blood collected will be 80 ml: 40 ml at baseline and 40 ml at follow-up. The total amount of urine collected will be 20ml: 10ml at baseline and 10ml at follow-up.

BWH will manage this protocol at baseline and post-randomization time points. BWH will be responsible for consenting participants and tracking, storing, and distributing COSMOS bloods and urine to appropriate laboratories. For assays related to COSMOS, BWH will coordinate with the labs for shipping, testing protocols and receipt of results data. One half of the specimen vials from WHI participants which are not used for the COSMOS study will be shipped to the WHI repository for storage at the conclusion of the COSMOS trial. These specimens will be inventoried and tracked in the WHI Study Tracking System (WHIST). Should the COSMOS blood collected for the parent trial fail to yield adequate lab results, BWH may request the CCC to ship a replacement vial for retesting.

9.0. Clinic-Based Sub-study

Additional measurements will be obtained from clinic-based visits at baseline and after 2-years follow-up for approximately 600 COSMOS participants residing in the greater Boston area at the Harvard Catalyst Clinical and Translational Science Center (CTSC). An equal number of women and men will be recruited. The clinic-based visits will include cognitive function assessments, physical assessments, blood pressure, and other measurements. A separate protocol and consent form will be developed and approved by the BWH IRB for the clinic-based COSMOS study visits.

9.1. Ancillary Studies

COSMOS Mind

COSMOS Mind cognitive data collection protocol will be modeled after the ongoing WHIMS-ECH and WHIMS-Y telephone-based protocols. Each assessment will be conducted by trained and certified examiners from the COSMOS-Mind Coordinating Center at Wake Forest and will be electronically audio-recorded for quality assurance. The interview consists of Story Recall 1 & II, Oral Trail Making test, Verbal Fluency, Number Span Test, Digit Ordering Test, Cognitive Change Index, Geriatric Depression Scale-Short Form and the Women's Health Initiative Insomnia Rating Scale. The interview will take approximately 45 minutes to complete.

Participants' Responses will first be recorded on paper versions of the test and later entered into a dedicated and secure data management website. A secure web-based call tracking system will be used to monitor participant contact information. Data will be managed from a secure ftp site at Wake Forest. The interview takes approximately 45 minutes.

COSMOS Web

COSMOS Web was designed as a ‘novel object recognition’ task. During the immediate matching trials, participants view a single complex stimulus for 10 seconds; following a 1 second delay they are asked to select which one of two objects is identical to the studied stimulus. Following all matching trials, participants are shown serially individual complex objects and asked to indicate whether each object is identical to any of the target stimuli studied during the immediate matching trials. On these recognition trials, half the stimuli are targets and half are foils. The primary dependent variable for the COSMOS Web is the mean reaction time (ms) for correct rejections of foil stimuli on the delayed recognition trials. Multiple versions (alternate forms) were created for repeat administration. There are 2 other cognitive assessments, Spatial Learning task and Flanker Task, in the web-based assessment. The interview takes approximately 25 minutes to complete.

COSMOS Eye

COSMOS Eye endpoints will be identified from reports on baseline and annual follow-up COSMOS questionnaires and from interim reports received through mail, email, or telephone conversations. Participants will be asked to provide the name(s) and contact information for treating physicians and written consent to obtain medical records. Treating physicians will be asked to complete a questionnaire related to the diagnoses or to provide relevant medical records. Participants with medical record confirmed diagnoses of AMD will be sent follow-up questionnaires to assess progression of AMD.

COSMOS Falls and Physical Performance

Falls and decreased physical performance are major public health problems among older adults. Each year in the U.S., 30% of adults aged ≥ 65 years fall, resulting in increased risk of injury, hospitalization and death. Several lines of evidence suggest that flavanols, commonly found in cocoa, confer beneficial effects on muscle function and physical performance. The effects of supplemental cocoa flavanols on recurrent falls, injurious falls resulting in healthcare utilization, and musculoskeletal health, will be examined in a cost-efficient ancillary study. The benefits and/or risks of multivitamins on musculoskeletal health among the study population will also be assessed.

Throughout the COSMOS intervention phase testing cocoa flavanols and a multivitamin, information on falls, fractures, and the use of medications for bone health was collected at baseline and on the periodic follow-up health questionnaires. Information from the main trial questionnaires will be used to determine whether cocoa extract reduces risk of recurrent falls (defined as 2 or more falls per year), injurious falls resulting in healthcare utilization, and fractures. A follow-up Fall Questionnaire will be sent to assess circumstances surrounding injurious fall(s) with healthcare utilization (e.g., reason for fall, location of fall) and medical records will be obtained for adjudication of the fall and fall-related injuries.

Information obtained from the clinic sub-cohort ($n = 603$) at baseline and 2-years post randomization will be used to test whether cocoa flavanols improve physical performance as assessed by grip strength (by dynamometer), walking speed (6 meters), and the Short Physical Performance Battery (SPPB) that includes tests of walking speed, standing balance, and chair stands. The effects of the study agents on changes in bone density will also be explored.

Results from analyses of the biospecimens will be used to examine effect modification by changes in flavanol concentrations on the fall(s) and fractures outcomes. Parallel analyses of the multivitamin supplement also will be performed. COSMOS provides a unique opportunity to maximally leverage existing resources to test, at minimal cost, efficacy of cocoa flavanols and/or a multivitamin on improving clinically meaningful musculoskeletal outcomes among older women and men in the U.S.

[name], Professor of Medicine at the David Geffen School of Medicine, UCLA, is an investigator on the COSMOS Falls and Physical Performance ancillary study to COSMOS. She will assist with design and conduct of the sub-study, adjudication of outcomes, interpretation of data, and presentation of the results. Mass General Brigham (MGB) staff will communicate with study participants to collect the sub-study questionnaires, signed authorization forms, and copies of medical records from healthcare providers. Once received, the records will be scanned onto a secure MGB network server managed by the Brigham and Women's Hospital Division of Preventive Medicine (DPM). Using an encrypted laptop, [name] will have access to identifiable data on the secure, web-based online medical record review/outcome adjudication system through the MGB Virtual Private Network (VPN). No data will be transferred to [name] or to the David Geffen School of Medicine at UCLA. A Research Data Sharing Plan will be put into place.

COSMOS Inflammaging and Epigenetic Aging

The effects of cocoa extract and multivitamins on longitudinal change in biological aging will be examined in an ancillary study conducted in collaboration with investigators from Augusta University. Accelerated epigenetic aging that comprises DNA methylation changes has recently emerged as a powerful, novel predictor for lifespan and health span, disease susceptibility, morbidity, and mortality risk. DNA methylation is a major epigenetic process that regulates gene expression and can be modified by different bioactive compounds in foods. In addition, human aging is characterized by chronic, low-grade inflammation, which has recently been termed inflammaging. Inflammaging is exemplified by mild chronic elevation in blood levels of C-reactive protein (CRP) and several cytokines such as interleukin-6 (IL-6) and tumor necrosis factor- α (TNF- α), which increase with aging. Inflammaging is a highly significant risk for both morbidity and mortality in the elderly, including cardiovascular disease.

Biospecimens collected from 600 COSMOS participants at baseline and after 1- and 2-years of follow-up will be analyzed for changes in markers of DNA methylation (including AgeAccelHorvath, AgeAccelHannum, LAgeAccelGrim, AgeAcfcelPhono, and DNAm TLadjAge) and inflammation. The relationship between cocoa extract and changes in epigenetic aging and inflammaging in relation to CVD will be evaluated. Parallel assessments of multivitamins on these markers of biological aging and CVD outcomes will also be performed. This ancillary study will provide valuable insights into the underlying molecular mechanisms for two popular supplements (cocoa and multivitamins) and holds great promise for targeting by nutritional interventions.

COSMOS Phase 1 Biomarker Assessments

BWH will send approximately 1,100 blood samples from 400 COSMOS participants to the University of California at Davis (UCD) for the measurement of key biomarkers linked with both the cocoa extract and multivitamin interventions. The assay results will be integrated into the analyses for the COSMOS Mind, Web, and coronavirus disease 2019 (COVID-19) projects. No additional samples will be collected from participants. No protected health information (PHI) will be sent to UCD.

COSMOS Phase 2 Biomarker Assessments

BWH will send approximately 11,600 spot urine samples from 6,795 COSMOS participants to the University of Reading (UR) for the measurement of key biomarkers linked with both the cocoa extract and multivitamin interventions. The assay results will be integrated into the analyses for the COSMOS interventions. No additional samples will be collected from participants. No protected health information (PHI) will be sent to UR.

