- 7) In a subset of equal numbers of female and male COSMOS respondents who provide baseline bloods and/or urine samples, cocoa extract and/or a daily multivitamin will significantly change blood and/or urinary levels of flavonoids or their metabolites, other pertinent nutritional biomarkers, and vascular/metabolic biomarkers from baseline to 1, 2, or 3 years of follow-up.

2.3. Tertiary Aim:

To assess whether the cocoa extract and/or a daily multivitamin exhibit synergistic effects on risk of major cardiovascular events or cancer, and if the effects vary by nutritional status or medication use.

2.4. Ancillary Aims:

- To assess whether the random assignment to daily cocoa extract, compared to placebo, has favorable effects on cognitive function over 3 years of follow-up in men and women.
- To assess whether daily cocoa extract and/or multivitamin have favorable effects on the risk of cataract and age-related macular degeneration (AMD).
- To assess whether daily cocoa extract and/or multivitamin have favorable effects on the risk of injurious fall(s) resulting in healthcare utilization, recurrent falls, physical performance, and fractures.
- To assess whether daily cocoa extract and/or multivitamin have favorable effects on inflammaging and epigenetic aging.

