4.4. Intervention

Cocoa Extract supplements: Active cocoa extract (600 mg/d of cocoa flavanols) and matching inert placebo with no cocoa flavanols will be provided by Mars Symbioscience. Participants will be asked to take two capsules per day, totaling 600 mg/d. After the COSMOS trial began, an advanced method to analyze cocoa flavanols was accredited by AOAC International as a First Action Official Method of Analysis <https://doi.org/10.1093/jaoacint/qsa132>). This updated method relies on a reference material (RM8403) recently standardized and made commercially available by the U.S. National Institute of Standards and Technology. While the actual cocoa flavanol content of the COSMOS intervention remained unchanged throughout the trial, the application of this new analytical method led to expected changes in how the total cocoa flavanol content is now reported. Applying AOAC 2020.05/RM8403 to the COSMOS intervention, the total cocoa flavanol content of the COSMOS intervention is now 500 mg/day. Reporting of (-)-epicatechin content remained unaffected. Going forward, we will therefore apply AOAC 2020.05/RM8403 and report that the COSMOS intervention tested 500 mg/day of cocoa flavanols, including 80 mg of (-)-epicatechin.

Multivitamin supplements: Active multivitamin (marketed as Centrum Silver™) and matching inert placebo will be provided by Pfizer Inc. Participants will take one tablet per day.

The manufacturers will perform quality control testing to ensure their products contain the correct amounts and are free of contaminants.

Study supplements will be packaged in calendar packs provided by Contract Pharmacal Corp (CPC) to promote adherence to daily dosing and facilitate self-reports of adherence to pill-taking. Participants will be instructed to take their study supplements at the same time each day.

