4.5. Randomization and blinding

Eligible participants will be randomized into one of 4 treatment arms in equal proportions:

- Active Multivitamin and Active Cocoa Extract;
- Active Multivitamin and Placebo Cocoa Extract;
- Placebo Multivitamin and Active Cocoa Extract;
- Placebo Multivitamin and Placebo Cocoa Extract.

The algorithm will use a randomized permuted block approach, stratified by (at minimum) sex, age group, and recruitment center (WHI or BWH). The date of randomized treatment assignment will be considered the formal enrollment date.

Whenever possible, household partners (e.g., spouse/partner) of a randomized COSMOS participant will be assigned to the same treatment group, as the corresponding randomized participant. To ensure balance within strata at the participant-level, the household partner will occupy the next available allocation with the same treatment, as the randomized participant. The strata of the household partner will be determined by the household partner's individual characteristics, and not the characteristics of the corresponding randomized participant.

BWH will receive all calendar packs for distribution to COSMOS participants and maintain blinding to treatment assignments.

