6.0. Sample size and power

Power calculations for the primary endpoints of major cardiovascular events and total invasive cancer are based upon a 2x2 factorial trial in approximately 22,000 participants, including 13,000 women aged ≥ 65 years and 9,000 men aged ≥ 60 years. Based on the log-rank test (equivalent to score tests for hazard ratios from a Cox model without covariates), Freedman³⁶ has shown that the power, $1-\beta$, of this test to detect a specified hazard ratio HR based on a two-sided test with significance level α is a simple function of the number of accrued events, m , in the two groups combined: $1-\beta = \Phi(\sqrt{m}(|HR-1|)/(|HR+1|) - Z_{1-\alpha/2})$, where Φ is the standard normal cumulative distribution function. The factorial design of this trial is motivated primarily by efficiency. The scientific justification for testing each intervention is independent of the other and stands alone. Therefore each comparison (multivitamins versus placebo and cocoa extract versus placebo) will be based on a marginal test (but controlling for the other intervention) at a level of $\alpha = 0.05$.

Estimates of study power and the expected numbers of confirmed, accrued events in Table 1 are based on the following assumptions: (1) independent and equal allocation of participants to each treatment; (2) an age distribution based on that observed among WHI women ≥ 65 years and men aged ≥ 60 years responding to the VITAL mailings; (3) annualized age-specific event rates based on observed rates during WHI and VITAL follow-up, adjusted for aging; (4) same event rates for men and women given that women are approximately 5 years older than men; (5) mean trial follow-up of 4 years, with nominal loss to follow-up as seen previously in WHI, VITAL, and mail-based trials by the BWH Division of Preventive Medicine; and (6) an average of 80% compliance. These assumptions remain the same as proposed for our original power calculations for 18,000 participants.

With approximately 22,000 randomized participants, there will be at least 80% power to detect a 11% relative hazard reduction in total CVD, and $>95\%$ power to detect such a reduction in the important composite of total CVD plus all-cause mortality with the expected number of events. Similarly, there would be at least 90% power to detect a 14% reduction in total cancer. Power for key secondary outcomes are highly dependent on the frequency of the events.

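### Section 9.1 examines effect modification of falls and fractures by post-randomization change in flavanol levels, which can suggest a modified effect where none exists

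*Protocol*

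**What the plan says.** Protocol section 9.1, under COSMOS Falls and Physical Performance, says that biospecimen results will be used to "examine effect modification by changes in flavanol concentrations on the fall(s) and fractures outcomes". The next sentence adds: "Parallel analyses of the multivitamin supplement also will be performed".

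Three other places show what kind of variable this change is:

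- Secondary hypothesis 7 (section 2.2) states that cocoa extract and/or the multivitamin "will significantly change blood and/or urinary levels of flavonoids or their metabolites".
- The same hypothesis gives the measurement window, ending "vascular/metabolic biomarkers from baseline to 1, 2, or 3 years of follow-up".
- Section 4.4 describes the control capsules as "matching inert placebo with no cocoa flavanols".

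Section 9.1 names no model, cut-point or causal method for this analysis, and no version that uses baseline concentration. The SAP does not cover the falls sub-study. The nearest safeguard is the general remark in section 10.0 that interactions are hypothesis generating.

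**The concern.** An effect modifier should be fixed before treatment starts, so that within each of its levels the arms still differ only by chance. Change in flavanol concentration is not fixed in this way. It depends on the arm, on whether the pills were taken, and on diet during follow-up.

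An active participant with little change is more likely than average to have stopped the capsules. A placebo participant with little change is an ordinary placebo participant. If those who stop capsules are also frailer, a comparison of arms at low change sets frailer active participants against typical controls. The contrast then mixes treatment with frailty.

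At stake is the interpretation of the sub-study. An apparent gradient by flavanol change could be read as biomarker support for a benefit of cocoa on falls and fractures, or as evidence against it, when it reflects who took the capsules.

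**Working it through.** **No figure to reproduce.** The documents give no sample size, power or error rate for this analysis. The check is therefore the design logic, followed by simulation.

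**Step 1: is the modifier affected by treatment?** Yes, on the protocol's own terms. Hypothesis 7 predicts the change, its window runs to years 1 to 3, and the placebo supplies no cocoa flavanols.

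**Step 2: how far can a null effect be distorted? Median split.** Equal arms follow section 4.5 ("Eligible participants will be randomized into one of 4 treatment arms in equal proportions"). A baseline fall risk of 0.30 follows section 9.1 ("30% of adults aged ≥ 65 years fall"). The rest is assumed. U is a standard normal health/adherence factor and A is the arm (1 = active):

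- change = A(1 + aU) + cU + N(0, s)
- logit P(fall) = log(0.3/0.7) + bU, with no treatment term

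| Setting | a | c | s | b | OR below median change | OR above |
|---|---|---|---|---|---|---|
| Strong links | 0.5 | 0.2 | 0.5 | −0.4 | 1.42 | 1.06 |
| Intermediate | 0.2 | 0.1 | 0.5 | −0.2 | 1.13 | 1.03 |
| Weak links | 0.2 | 0.05 | 1 | −0.2 | 1.05 | 0.99 |
| U does not affect falls | 0.5 | 0.2 | 0.5 | 0 | 1.00 | 1.00 |
| U does not affect change | 0 | 0 | 0.5 | −0.4 | 1.00 | 1.00 |

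The overall odds ratio is about 1.00 in every row. Repeat runs of the strong setting gave 1.41 to 1.44 below the median and 1.04 to 1.07 above it. Both strata can exceed 1.00 because membership differs by arm: in the strong setting the lower half holds 24% of the active arm and 76% of the placebo arm. Splitting the same data at a baseline value gives about 1.00 in both halves, also when the baseline value itself depends on U.

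The strong setting is demanding. In the active arm U explains (0.5 + 0.2)² / [(0.5 + 0.2)² + 0.5²] = 0.49/0.74 = 66% of the variance in change. In the weak setting it explains (0.2 + 0.05)² / [(0.2 + 0.05)² + 1²] = 0.0625/1.0625 = 6%.

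**Step 3: how often would an interaction test reject falsely?** The model is logistic for any fall, with arm, change and arm × change, a two-sided Wald test at 0.05, and 1,500 replicates per setting. Inputs from the documents are equal arms, 30% fall risk and "an average of 80% compliance" (section 6.0), read here as 80% of participants complying. Section 9.1 mentions about 11,600 urine samples from 6,795 participants. With one baseline sample each, that leaves at most 11,600 − 6,795 = 4,805 follow-up samples. At one to three follow-up samples per person, about 4,800 to 1,600 people have a change value.

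Assumed: frailty raises non-compliance and falls by the odds ratios shown (per SD), and compliant active participants have the rise shown.

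| OR, non-compliance | OR, falls | Rise (SD) | n = 1,600 | n = 2,400 | n = 4,800 |
|---|---|---|---|---|---|
| 1 | 2 | 2 | 4% | 5% | 4% |
| 2 | 1 | 2 | 4% | 5% | 5% |
| 1.5 | 1.5 | 2 | 6% | 7% | 8% |
| 2 | 2 | 2 | 13% | 17% | 30% |
| 3 | 2 | 3 | 25% | 37% | 66% |

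The true odds ratio is 1.00 in all rows. In the fourth row the apparent odds ratio is about 1.14 at zero change and 0.97 at a 2 SD rise, which would look like a benefit confined to those whose levels rose. With a constant true odds ratio of 0.85 and the same links, the test still rejects in 14% to 32% of trials. A baseline modifier rejects in about 4% to 6% throughout.

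**The case against.** The case for leaving the text alone has real substance.

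- **The bias is conditional.** It needs a common cause of flavanol change and falls, and the documents give no such association. A reader might infer that the analysis is bound to give a spurious dose-response. The documents do not support that: with either link absent, the test keeps its 5% level. A common cause is nevertheless plausible, and the SAP treats non-compliance as informative when it weights its per-protocol analyses for dependent censoring.
- **The text is one summary sentence.** It says examine, not test, and the authors may have meant exposure-response or mediation. Section 4.3 provides for separate ancillary protocols as appropriate, so a fuller plan may exist. But the words used are effect modification, and section 5.4 speaks of mediation for the inflammaging study, so the protocol distinguishes the two.
- **The multivitamin extension is an inference.** The sentence on parallel analyses names no biomarker and may refer to the falls analyses generally. A reader might take it as a commitment to the same method, but the text does not go that far.
- **The distortion need not mirror itself.** A reader might expect opposite biases at low and high change. In the strong setting both odds ratios exceed 1.00, so only a difference between strata can be claimed.
- **The analysis is exploratory.** The caution in section 10.0 tempers the interpretation, but it does not remove a bias that becomes easier to detect as the sample grows.

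**Conclusion.** The concern holds as a conditional one. As written, section 9.1 conditions on a variable that follows randomization and is expected to respond to cocoa. If frailty, adherence or diet drives both that variable and falls, the analysis can show a modified effect where there is none. Under a true null the distortion ranged from slight (odds ratios 1.05 and 0.99) to clear (1.42 and 1.06), and it vanished without a common cause. These sizes rest on assumed associations and on a median split and logistic models that the protocol does not specify.

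A reader might infer that the sub-study's answer on falls, or the trial itself, is compromised. It is not. The comparisons of falls and fractures by randomized arm and the primary and secondary trial outcomes do not use this variable. The point is confined to an ancillary analysis in the subset with repeat specimens.

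**What to change.** In section 9.1 or the ancillary analysis plan:

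1. Use pre-randomization flavanol concentration, or dietary flavanol intake from the run-in food frequency questionnaire (section 7.2), as the effect modifier.
2. If the effect of achieved change is wanted, label it as mediation, exposure-response, instrumental-variable (with assignment as the instrument) or principal-stratum analysis, and state its assumptions.
3. State which falls are counted relative to the follow-up sample, because falls before that sample could themselves affect the measured change.
4. Apply the same rule to multivitamin biomarkers if the parallel analyses use their change.

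The cost is a few sentences. Baseline specimens were planned for about 3,500 women and 3,500 men, and only a subgroup gives follow-up samples (section 8.0), so a baseline modifier also keeps more participants and avoids selection after randomization. The drawback is that it asks whether initial flavanol status alters the effect of cocoa, which is a slightly different question from the effect of the exposure achieved.
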